## **2-For patients with large vessel vascular disease**

### A Improvement in relevant symptoms

- a. Localised pain (by using physician and patient's global assessment with visual analog scale (VAS))
- b. Abdominal pain, (by using physician and patient's global assessment with visual analog scale (VAS))
- c. Calf thickness, (by measuring)
- d. Hemoptysis (yes/no)

### B Improvement in systemic inflammatory findings (CRP, ESR, SAA)

### C Any improvement in radiological findings depending on the involved vessels (MR, CT or Doppler findings)

**Complete response** will be defined as clinical and laboratory improvement based on >50% improvements in patient's and physician's global assessments by using VAS, and >50% reduction in CRP values; along with stable or >20% reduced aneurysm size in patients with arterial involvement, and stable or >20% reduced calf swelling in patients with lower extremity venous thrombosis.

**Partial response** will be defined as clinical and laboratory improvement based on observing an improvement between 20-50% according to patient's and physician's global assessments by using VAS, 20-50% reduction in CRP values; along with stable or less than 20% reduced aneurysm size in patients with arterial involvement, and stable or less than 20% reduced calf swelling in patients with lower extremity thrombosis.

**Non-response** will be defined as observing no or less than 20% clinical improvement by patient's and physician's global VAS or worsening of clinical findings, no change or increase in acute phase response, increase in aneurysm size for patients with arterial involvement or progression of venous thrombosis in patients with venous involvement.

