**Partial response** will be defined as clinical and laboratory improvement based on observations of an improvement between 20-49% according to patient's and physician's global assessments by using VAS, 20-49% reduction in CRP values; along with stable or less than 20% reduced aneurym size in patients with arterial involvement, and stable or less than 20% reduced calf swelling in patients with lower extremity thrombosis.

**Non-response** will be defined as observing no or less than 20% clinical improvement by patient's and physician's global VAS or worsening of clinical findings, no change or increase in acute phase response, increase in aneurysm size for patients with arterial involvement or progression of venous thrombosis in patients with venous involvement.

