#### **For Vascular Disease :**

1)Patients experiencing an acute exacerbation of vascular disease within the last month, involving

- d. Large arteries (abdominal aorta, pulmonary arteries, extremity arteries)
- e. Large veins (deep vein thrombosis of extremities, caval vein thrombosis, dural sinus thrombosis)
- f. Compatible radiological findings (spiral CT, MR, or Doppler ultrasonography)

**2)** Patients aged over 18-60 BD fulfilling the International Study Group (ISG) criteria, who have exacerbation of large-vessel vascular disease and/or parenchymal neurologic disease *with in last month*.

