### **5.7.2 Inflammation markers**

The following markers of inflammation, Erythrocyte Sedimentation Rate (ESR), C-reactive protein (CRP) and serum amyloid A (SAA), will be performed at all scheduled visits.

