## **5.9 Efficacy**

### **5.9.1 Resolution of Attacks**

#### **The definition of the attack**

**For Vascular Disease:** Recent Onset symptomatic Venous Thrombosis or Arterial Aneurysm.

**For Neurologic Disease:** An acute/subacute neurological syndrome including any of hemiparesis, ataxia, dysarthria within the first month of onset of neurologic manifestations.

**Primary endpoint:** Resolution of acute exacerbation findings related to BD based on achievements in any of the following items without deterioration on day 30:

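### Vascular complete and partial response both need a percentage fall in CRP, but entry needs no raised CRP, so a recovered patient whose CRP was normal throughout fits no response category

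*Combined protocol and SAP*

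**What the plan says.** Vascular response is defined in sections 2.1 and 5.9.1. Complete response combines at least (2.1) or more than (5.9.1) 50% improvement on the patient's and physician's global VAS with ">50% reduction in CRP values; along with stable or >20% reduced aneurysm size in patients with arterial involvement", or the matching calf-swelling condition for leg-vein thrombosis. Partial response combines a VAS improvement in a middle band with "20-49% reduction in CRP values" in 2.1, or "20-50% reduction in CRP values; along with stable or less than 20% reduced aneurysm size in patients with arterial involvement" in 5.9.1. The non-response list opens with absent or under-20% VAS improvement and includes "no change or increase in acute phase response". None of these definitions has a provision for CRP that is normal at baseline, and none lets ESR or SAA stand in for CRP.

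Vascular entry (section 4.1) needs an exacerbation within the past month and "Compatible radiological findings (spiral CT, MR, or Doppler ultrasonography". The attack is defined in 5.9.1 as "Recent Onset symptomatic Venous Thrombosis or Arterial Aneurysm". Neither sets a threshold for CRP, ESR or SAA, and no exclusion criterion removes patients with normal CRP.

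Section 8.4.1 lists the percentage of complete responders first among the primary variables. Section 8.4.2 aims for at least 50% response in at least half the patients. Under 3.1 and 5.5.5 the month-1 class also decides the dosing schedule and whether the patient continues.

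**The concern.** A percentage-fall condition presumes that there is something to reduce. A vascular patient can qualify on symptoms and imaging, up to a month after the exacerbation began, with CRP already in the normal range. If that patient then recovers completely, the plan still asks for CRP to halve. Whether it does depends on assay and biological variation within the normal range, or on how low the laboratory reports, and not on clinical benefit.

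The primary response percentage could therefore miss some of the best clinical outcomes. With no written rule for these patients, the physician would have to assign a class by judgement, in an open-label trial without an adjudication committee (7.5).

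**Working it through.** The plan derives no figure on this point: section 8.7 sets ten patients without a calculation. The check is first logical, then illustrative.

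**1. Logic.** Take a vascular patient with normal baseline CRP, full VAS recovery, stable aneurysm or calf size, and CRP unchanged at Day 30.

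| Category | VAS | CRP | Vessel or calf | Result |
|---|---|---|---|---|
| Complete | met | not met (no 50% fall) | met (stable) | fails |
| Partial | not met (above the band) | not met (no 20-50% fall) | met (stable) | fails |
| Non-response | not met (improved by more than 20%) | met (unchanged) | not met (no progression) | one limb only |

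**2. Chance of meeting the CRP condition through noise.** Assume log-normal CRP around an unchanged level with within-person CV of 0.3, 0.4 or 0.6; the documents give no CV. The SD of the log ratio of two readings is s = √2 × √ln(1 + CV²), and P(ratio ≤ r) = Φ(ln r / s).

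| CV | s | P(fall ≥ 50%) | Misses complete-response CRP condition | P(fall ≥ 20%) |
|---|---|---|---|---|
| 0.3 | 0.415 | 4.7% | 95.3% | 29.5% |
| 0.4 | 0.545 | 10.2% | 89.8% | 34.1% |
| 0.6 | 0.784 | 18.8% | 81.2% | 38.8% |

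A fall between 20% and 50% (29.5 − 4.7 = 24.8% of patients at CV 0.3; 38.8 − 18.8 = 20.0% at CV 0.6) does not help the fully recovered patient, whose VAS improvement lies above the partial band. The relevant miss rate is therefore 81-95%.

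**3. Reporting limit.** The largest observable fall from baseline b with reporting limit L is 1 − L/b. With assumed L = 3 mg/L, a baseline of 4 gives 1 − 3/4 = 25% and a baseline of 5 gives 1 − 3/5 = 40%; neither reaches 50%. With assumed L = 1 mg/L, a baseline of 4 gives 1 − 1/4 = 75%. A normal baseline makes the class unreliable, but does not always make complete response impossible.

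**4. Effect on the result.** One patient in ten is 1/10 = 10 percentage points. Read the 8.4.2 criterion as at least 5 complete responders of 10, assume a true complete-recovery rate of 70%, and let k patients be wholly unable to meet the CRP condition. Then the chance of success is P(Binomial(10 − k, 0.7) ≥ 5), and the expected complete-response rate is 70% × (10 − k)/10.

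| k | Chance of meeting criterion | Expected complete-response rate |
|---|---|---|
| 0 | 0.953 | 70% |
| 1 | 0.901 | 63% |
| 2 | 0.806 | 56% |
| 3 | 0.647 | 49% |

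At an assumed 60% recovery rate, the chances are 0.834, 0.733, 0.594 and 0.420. Treating these patients as wholly unable to meet the condition somewhat overstates the loss, because step 2 leaves 5-19% meeting it by chance.

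**The case against.** The strongest counter-argument is that the endpoint stated in 2.1 and 5.9.1 is improvement in any one of several items without deterioration. Symptom VAS and imaging are among them, so the recovered patient counts as resolved with no CRP fall. That is correct. But the documents never say how this endpoint relates to the three response classes, and 8.4.1 analyses complete responders. The gap in the classification stands.

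Two stronger readings are tempting. A reader might infer that the patient is classed as a non-responder and dropped at month 1. The text does not support this: how the limbs of the non-response list combine is unclear, and the list opens with a VAS limb that this patient does not meet. Sections 3.1 and 5.5.5 drop non-responders and deteriorating patients; they do not mention a patient who fits no class. A reader might also infer that all later information is lost. Section 5.7 schedules a visit 8 weeks after the last dose, with the final-visit assessments, for anyone who stops or withdraws early.

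It is also fair to say that the trial is exploratory and unpowered, that the neurologic complete and partial definitions do not use CRP, and that treatment might lower CRP even within the normal range, which the noise model ignores. These points limit the weight of the finding without removing it.

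**Conclusion.** The concern holds in this form: the vascular definitions give no usable class to a fully recovered patient whose CRP was and stays normal, so that patient cannot reliably count as a complete responder. This follows from the wording alone.

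The size is illustrative. About 81-95% of such patients would miss the complete-response CRP condition, given assumed CVs of 30-60% and no true change in CRP. The number affected cannot be derived, because neither the vascular share of the ten patients nor the baseline CRP distribution is given; it could be zero. Each affected patient moves the percentage by 10 points against the 50% criterion. The change should be made before the Day 30 classes are analysed.

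**What to change.** For the response classification used in the analysis (2.1, 5.9.1 and 8.4.1):

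- Apply the percentage CRP condition only when baseline CRP is above the laboratory upper limit of normal, and state that limit.
- When baseline CRP is at or below the limit, replace the percentage condition for complete and partial response with CRP remaining at or below it, and do not count an unchanged acute phase response towards non-response.
- Report how many vascular patients were classified under each version.
- State how the any-item endpoint relates to the three classes.

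Because the Day 30 class also governs dosing and continuation in 3.1 and 5.5.5, the sponsor must reconcile those passages with the revised classification. No clinical rule is proposed here.

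The cost is a wording change and one derivation rule. No new data are needed, since "C-reactive protein (CRP) and serum amyloid A (SAA), will be performed at all scheduled visits". The drawback is that, in patients with normal CRP, the class rests mainly on VAS and on imaging or calf measurement. A step also remains at the limit: a patient just above it whose CRP normalises with a fall of, say, 30% would still miss complete response, which is why both counts should be reported.

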### **5.9.5 Improvement / Changes in Symptoms**

Headache; will be assessed by Visual Analog Scale, ranging from 0 to 10 cm, 0 indicating the best score and 10 the worst score, and it will be assessed by the patients and physicians during each visit.

Localized Pain; will be assessed by Visual Analog Scale, ranging from 0 to 10 cm, 0 indicating the best score and 10 the worst score, and it will be assessed by the patients and physicians during each visit.

Abdominal Pain will be assessed by Visual Analog Scale, ranging from 0 to 10 cm, 0 indicating the best score and 10 the worst score, and it will be assessed by the patients and physicians during each visit.

Ataxia Improvements / Changes will be assessed by Physician Global Assessment.

Calf thickness / swelling will be calculated by tape measure.

Hemoptysis will be assessed by (Yes / No) scale.

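### The calf-swelling item for leg-vein thrombosis is not ordered: on one reading of *stable*, an unchanged leg satisfies complete response and a partly reduced one does not; on another, the 20% cut-off does nothing

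*Combined protocol and SAP*

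**What the plan says.** Section 5.9.1 classifies patients with large-vessel disease as complete, partial or non-responders at Day 30. For leg-vein thrombosis the parts are:

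- **Complete response:** ">50% improvements in patient's and physician's global assessments by using VAS", ">50% reduction in CRP values", and a calf that is "stable or >20% reduced calf swelling in patients with lower extremity venous thrombosis".
- **Partial response:** 20–50% improvement on the same VAS assessments, "20-50% reduction in CRP values", and a calf that is "stable or less than 20% reduced calf swelling in patients with lower extremity thrombosis".
- **Non-response:** little or no VAS improvement or clinical worsening, no fall in the acute-phase response, or "progression of venous thrombosis in patients with venous involvement". No calf threshold appears here.

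Section 2.1 repeats the scheme with different boundaries: at least 20% for the calf in complete response, at least 50% for VAS and CRP, and 20–49% for partial response.

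On measurement, section 5.9.5 says only "Calf thickness / swelling will be calculated by tape measure", and the symptom list in 5.9.1 calls the item calf thickness. Neither section names a level on the leg, a comparison with the other leg or a pre-attack value, or a formula for the percentage.

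The percentage of complete responders is the first variable listed in section 8.4.1. Section 8.4.2 sets an efficacy target in terms of at least half of the patients. Section 8.7 gives 10 patients. Sections 3.1 and 5.5.5 make each patient's further course depend on the same Day 30 category.

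**The concern.** A response scale should never rank no change above improvement. Here the complete-response item accepts two separate regions, unchanged and reduced by more than 20%, and may leave out the region between them. The partial-response item accepts *stable* as well, so for an unchanged leg the calf does not help to tell complete from partial response.

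The choice of scale can make this worse. Most of a calf's circumference is normal leg, so a percentage of circumference is much smaller than the same change expressed as a percentage of swelling. Real recovery could then fall in the omitted region.

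At stake is the Day 30 category of any patient with leg-vein thrombosis, and through it a primary variable in a very small study. The trial is open-label and section 7.5 provides for no adjudication committee, so each investigator would have to settle the meaning alone.

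**Working it through.** The plan gives no derivation for the 20% cut-off, so there is no figure to reproduce. The check applies the printed rules and then the arithmetic of the two possible scales.

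**1. The rule under different meanings of *stable*.** Illustration on whole circumference: assumed normal calf 36 cm, swollen to 40 cm at Day 0. Fall = (40 − Day 30 value)/40.

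| Day 30 calf | Fall | Complete item, stable = within 2% | Complete item, stable = within 5% | Complete item, stable = not increased |
|---|---|---|---|---|
| 40 cm (no change) | 0% | met | met | met |
| 39 cm | 2.5% | failed | met | met |
| 38 cm | 5.0% | failed | met | met |
| 37 cm | 7.5% | failed | failed | met |
| 36 cm (full recovery) | 10.0% | failed | failed | met |

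The partial-response item is met in every row under all three meanings. With a tolerance, the order is wrong. With *not increased*, the order is acceptable but the 20% figure plays no part, because every reduction already passes.

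**2. The whole category.** Take the 36 cm patient, with VAS and CRP improvements above 50% and *stable* meaning near-unchanged:

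- Complete response fails on the calf.
- Partial response fails because VAS and CRP are above its 20–50% band.
- Non-response fails because nothing has worsened or stayed flat.

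No category applies. The mirror case also has no category: VAS and CRP improved by 20–50% with a calf reduced by more than 20% is too good on the calf for partial response and not good enough on VAS and CRP for complete response.

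**3. Whole-circumference scale.** With normal circumference c and excess e, full resolution is a fall of e/(c + e). Calf sizes are assumptions, since the documents give none.

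- c = 40, e = 2: 2/42 = 4.8%
- c = 36, e = 4: 4/40 = 10.0%
- c = 34, e = 6: 6/40 = 15.0%
- Wider range, c = 30–45 and e = 1–6: from 1/46 = 2.2% to 6/36 = 16.7%

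A 20% fall requires e/(c + e) = 0.20, so e = 0.25c: 8.5 cm for c = 34, 9 cm for c = 36 and 10 cm for c = 40.

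**4. Excess scale.** If swelling is the excess over the other leg, full resolution is e/e = 100% and passes. The cut-off is 0.2e, which is 0.4 cm for e = 2 and 1.2 cm for e = 6. The gap between unchanged and 20% remains: a 10% reduction of the excess still fails the complete item, unless it counts as stable, while no reduction passes.

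**5. Boundary.** A reduction of exactly 20% meets the complete item in section 2.1. In section 5.9.1 it meets neither the complete nor the partial limb, unless it is called stable.

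**6. Size.** One patient of 10 is 1/10 = 10 percentage points, and the 50% target is 5 of 10.

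**The case against.** The strongest reply is that *stable* naturally means not increased. The same sentence uses the word for aneurysm size, where the matching non-response limb is an increase. On that reading the calf item is a guard against worsening, full recovery passes and an enlarged leg fails. This is a fair reading and may be the intended one. It leaves the 20% cut-off without function in the complete-response item, and the text does not say that it is the meaning.

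Three stronger conclusions are tempting, and the documents do not support them:

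- **That full resolution can never reach 20%.** The plan does not say that the percentage is of whole circumference. Swelling can be read as excess, where full resolution is 100%. Even on circumference, an excess of 10 cm on a 36 cm calf gives 10/46 = 21.7%.
- **That the item tests nothing.** On the lenient reading it still excludes an increase. Complete response also needs the VAS and CRP improvements, so the calf never confers it alone.
- **That a 40 cm calf could grow by 8 cm (20%) and the patient still be a responder.** Even if *stable* meant within 20%, the endpoint requires no deterioration, and worsening or progression of thrombosis counts as non-response.

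It is also true that the calf is not the only structural evidence. Radiological improvement is a listed endpoint item, and section 5.9.6 provides Doppler and/or MRI for deep vein thrombosis. The study is exploratory and unpowered. These points limit the consequence but do not put the categories in order.

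**Conclusion.** The concern holds as a fault of ordering and definition. It does not show that the criterion is unattainable. The ordering fault needs no assumption about calf size: it follows from the printed rules whenever *stable* means essentially unchanged, on either scale. If *stable* means not increased, what remains is a redundant cut-off.

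The further claim, that full recovery itself lands in the failing band, rests on two assumptions: that the percentage is taken on whole circumference, and that swelling is moderate (normal calf 34–40 cm, excess 2–6 cm, giving 4.8% to 15.0%).

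The effect is 10 percentage points of the response rate per misclassified patient. The item applies only to leg-vein thrombosis. Enrolment also covers neurologic and arterial disease and caval and dural sinus thrombosis, so the number affected among the 10 is unknown and could be zero. It should be corrected because it feeds a primary variable and the correction is cheap.

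**What to change.** Amend sections 5.9.5, 5.9.1 and 2.1 together:

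1. Define calf swelling as affected minus unaffected circumference at the same marked level, measured at Day 0 and Day 30. For bilateral disease, use the change from Day 0 at the marked level, with a stated margin in centimetres.
2. Define *stable* by a stated measurement-error margin, fixed before any patient is classified.
3. Rewrite the calf items so that any reduction ranks at least as high as no change, full resolution always meets the complete-response item, and complete and partial response do not overlap. Either the item is a plain no-increase condition and the 20% is dropped, or it is graded and no change no longer satisfies the higher grade. The sponsor should choose one and say which category applies when the calf, VAS and CRP parts disagree.
4. Reconcile the boundary: at least 20% in section 2.1, more than 20% in section 5.9.1.

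Defining the between-leg difference alone is not enough. It makes 20% reachable, but a smaller reduction could still fail where no change passes.

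The cost is one extra tape reading of the other leg per visit and a written amendment with the approvals required by section 10.1. The gain is confined to patients with leg-vein thrombosis.

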## **5.9.2 Preservation of Remission within 12 months :**

Investigators will question absence / presence of attack during each visit. Normalization of inflammatory markers, improvements in symptoms will be recorded during each visit.

### **5.9.3 Overall Disease Activity Measures**

Using Behcet Disease Current Activity Form (BDCAF) to collect general information about the disease course and progress. The patient will fill the form starting from baseline till the end of the study in every treatment day. The scores will be analysed at Day 30, 90, 180 and 360.

### **5.9.4 Steroid Tapering**

Prednisolone dosage should be 20 mg or less at baseline, and it should not be increased during the trial.

At the end of Day 30, complete responders begin to decrease the steroid doses. Tapering target will be 2,5 mg for every 2 weeks. At Day 120, patients expected to use prednisolone no more than 5 mg / day.

### **5.9.5 Improvement / Changes in Symptoms**

Headache; will be assessed by Visual Analog Scale, ranging from 0 to 10 cm, 0 indicating the best score and 10 the worst score, and it will be assessed by the patients and physicians during each visit.

Localized Pain; will be assessed by Visual Analog Scale, ranging from 0 to 10 cm, 0 indicating the best score and 10 the worst score, and it will be assessed by the patients and physicians during each visit.

Abdominal Pain will be assessed by Visual Analog Scale, ranging from 0 to 10 cm, 0 indicating the best score and 10 the worst score, and it will be assessed by the patients and physicians during each visit.

Ataxia Improvements / Changes will be assessed by Physician Global Assessment.

Calf thickness / swelling will be calculated by tape measure.

Hemoptysis will be assessed by (Yes / No) scale.

